### Experimental virtual supermarket

This study will be undertaken in a virtual reality environment that mimics the aisles, shelve and position of food products of a real supermarket. This virtual environment will be developed by our partner STRATEGIR under Oculus Quest 2 (https://www.strategir.com/fr/). The food products available in the virtual supermarket will be real products that can be found in three French supermarkets (*Intermarché, Carrefour and Picard*). Participants will see the front of the products on the shelves in the same size as if they were in a real supermarket. With a hand controller, participants will be able to navigate in the virtual supermarket, come closer, seize and examine closely the products they would like to choose. Once a product is selected, they will have the option to either put the product in their shopping cart or to put it back on the shelf.

### Choice of the foods available in the supermarket

Based on a recent study carried out in a virtual supermarket (Melendrez et al. *working paper*), four food groups will be included in our virtual supermarket: "Meat, egg, fish and substitutes", "legumes", "vegetables" and "starchy foods". The number of foods composing each category, for each task of the shopping scenarios ("everyday scenario" and "environmentally-friendly scenario"), is described in **Table 2**. The foods included in each category are either canned, dry, fresh, or frozen.

As participants will be asked to select foods for a main dish only, the items included are all savoury foods. They are typical foods that can be part of a main dish. We will focus on the main dish as it is the meal item where we found the greater variability in terms of environmental impact, as compared with starters and desserts. Food sub-categories were chosen with distinct environmental impacts to maximise the likelihood of substitutions between food products of contrasted environmental impact.

Tasks for each shopping scenario	Main Food Groups	Food Sub-groups	Number of products included
	Starchy foods	-	12
	Vegetables	-	12
	Legumes	-	12
Task 1:		Beef and lamb	6
Home-cooked dish	Meat, eggs, fish and substitutes	Other meat	6
		Fish	6
		Other animal products	6
		Plant-based meat substitutes	6
	Beef and lamb	/	6
	Other meat	/	6
Task 2: Ready to eat dish	Fish	/	6
	Vegetarian dishes (with animal products)	/	6
	Vegan dishes (without animal products)	/	6

#### Table 2. Foods included in the virtual supermarket

### Availability and placement of the products in the virtual supermarket

The first rule we adopted to create our virtual environment was to keep the same types of shelves as in a real supermarket. The shelves are defined by the storage method of the products. 4 types of shelves have been identified:

- With canned products
- With dry products
- With fresh products
- With frozen products

As in a real supermarket, within each shelf, we grouped products from the same food category (**Table 3**). To control for availability effect, we chose to allocate the same space to each product.

Task 1: Home-cooked dish				Task 2	Ready to e	at dish	
Food ca	tegories	Canned products	Dry products	Fresh products	Ready-to-eat dish category	Frozen products	Fresh products
	Dairy products	0	2	4	Dairy products	4	2
Meat, egg,	Poultry and pork	0	0	6	Poultry and pork	3	3
fish and substitutes	Cow or sheep meat	0	0	6	Cow or sheep meat	3	3
	Sea food	2	0	4	Sea food	4	2
	Plant-based substitutes	0	2	4	Plant-based substitutes	4	2
	Vegetables	5	0	7	Total	18	12
	Legumes	4	6	2			
	Starchy foods	1	10	1	]		
	Total	12	20	34			

**Table 3.** Number of products composing each shelf of the virtual supermarket.

### Intervention (environmental label)

As mentioned in the design of the experiment, an environmental label will be added to the front of the pack of the 96 food items included in the virtual supermarket.

### Development of an environmental score:

In order to identify the environmental impact of the 96 foods included in the virtual supermarket, we matched each experimental food product with items in Agribalyse database. To create our environmental score, we used the PEF, *Product Environmental Footprint,* score recommended by the European Commission (Pant et al., 2019). This score has the aim to evaluate the environmental impact of a food product based on 16 indicators such as climate change (kg CO2 eq), ozone depletion (kg CFC-11 eq), marine eutrophication (kg N eq), land and water use or acidification (mol H+ eq). These 16 indicators are calculated throughout the life cycle of the products. In order to obtain a unique PEF score, the indicators are weighed according to a method described by the European Commission (Pant et al., 2019). PEF scores for the foods present in the Agribalyse database are expressed in mPt for 1 kg of product. Pt means "eco-indicator point" and on a scale, 1 mPt represents the mean annual environmental load of an average European inhabitant.

In order to highlight PEF score variability across the different products presented in the virtual supermarket we created a segmentation of this score into five modalities. We defined the cut-offs

<sup>2 Agribalyse is a database with the environmental impact, calculated thanks to a life cycle analysis, of 2480 different foods created by the French Environmental and Energy Management Agency (ADEME). https://agribalyse.ademe.fr/app/aliments

across modalities as the quintile values from a larger selection of similar foods from Agribalyse database. For the first shopping task (choice of 3 ingredients to compose a home-cooked dish), we created quintiles for the PEF score of 1655 foods that correspond to the food groups included in the virtual supermarket (**Table 4**). We replicated this method for the second task (choice of a ready-to-eat dish among 30 products). The quintiles were therefore calculated for the 281 foods from Agribalyse database with corresponding food groups (**Table 4**).

The process for the creation of the environmental score, explained for the first shopping task, is summarised **Figure 2**.

[figure not shown]
**Table 4.** Food groups from the Agribalyse database that are common with the food items included in

 the virtual supermarket

Food groups from Agribalyse used to create a list of foods from which we created quintiles				
Task 1: Choice of 3 ingredients to compose a home-cooked dish among 66 products	Task 2: Choice of a ready-prepared dish among 30 products			

 
Fruits, vegetables, legumes, nuts and seeds
 
Cereal products
 
Milk and dairy products
 
Meat, egg and fish
 
Starters and dishes
 
				
These food groups represent:				
N=1655 foods N=281 foods				

**Table 5.** Limits of the quintiles created for the PEF scores of the different foods selected.The values in the following table are PEF scores expressed in (mPt/kg of product)

Ingredients	Ready-to-eat dishes
1655 foods	281 foods
0 < Q1 ≤ 0,17	0 < Q1 ≤ 0,20
0,17 < Q2 ≤ 0,35	0,20 < Q2 ≤ 0,36
0,35 < Q3 ≤ 0,62	0,36 < Q3 ≤ 0,46
0,62 < Q4 ≤ 1,36	0,46 < Q4 ≤ 0,84
1,36 < Q5 ≤ 6,09	0,84 < Q5 ≤ 3,23

### Figure 2. Creation of an environmental score for the label

#### Creation of an environmental label:

Since no environmental label design is currently being used in France for food products, we created a design considering previous findings regarding the most effective label designs.

The ideal label proposed by Carrero and collaborators is "traffic-light labels" (Carrero et al., 2021). It has been shown that green is often seen as a validation ("go") and a positive colour whereas red is associated with negative aspects and danger (Schuldt, 2013). This was put forward in research preceding the adoption of a nutritional front-of-pack label (Ducrot et al., 2015).

In September 2020, the French Agency for ecological transition (ADEME) published a design for a label assessing the environmental impact for the life cycle analysis of products or services (ADEME, 2020), see **Figure 3**. The colour was changed to obtain a "traffic light label" since it is considered as the best option to increase understanding and therefore behaviour change in consumers, see **Figure 3**. The label will be placed on the bottom part of the products.

[figure not shown]

Figure 3. Design of the environmental label inspired by the French environmental label of ADEME

### Questionnaires after the shopping experience

After the shopping experience, participants will be asked to complete one questionnaire with the virtual reality headset and four questionnaires on a separate computer (Qualtrics). These questionnaires will be presented in the following order:

- After the four shopping tasks, participants will be asked to evaluate their familiarity and liking of the eight products selected under the virtual reality headset. The eight products will successively appear under the headset and participants will give a familiarity score (frequency of consumption of a similar product, ranging from "never" to "very often") and a liking score (score ranging from 1 to 10) for each product.
- 2) An investigation questionnaire will then be presented to participants on a computer to identify aim-guessers and record participants' feedback about their experience in the virtual supermarket. We will use questions adapted from the *presence questionnaire* used in previous studies (Schnack et al., 2019; Witmer et al., 2005). We will ask participants to evaluate, for each scenario, the importance of the presumed price, taste, packaging size, nutritional quality and environmental impact when making their choices ("not influenced" to "very influenced" by each criteria). For participants in the "label condition", we will also investigate if they paid attention, understood and used the environmental label while selecting products. Participants in the "no label condition" will also be asked if they noticed the presence of an environmental label in the virtual supermarket (*manipulation check*) and if they understand the meaning of the environmental label (displayed in the questionnaire). We will also ask questions to investigate what participants understood when asked to choose an environmentally-friendly dish.
- 3) From this will follow a food choice motivation guestionnaire. We will use the adaptation of the Food Choice Questionnaire (Steptoe et al., 1995) for the French population (Cottet et al., 2017). This version includes 24 items that are grouped in 9 subscales (health, convenience, sensory appeal, natural content, ethical concerns, weight control, mood, familiarity and price). In order to have a better understanding of the sustainability motives consumers have for selecting their food, we will also ask independently the "Environmental welfare" subscale from the recently published Sustainable Food Choice Questionnaire (SUS-FCQ) (Verain et al., 2021). This subscale is composed of 5 items and its reliability was considered, by its authors, high enough to be used independently. The 5 items were translated in French and back-translated to English. For each item, participants will be asked to give a score ranging from 1 to 4 (1= not at all important, 2= a little important, 3= moderately important and 4 = very important). We will calculate the average scores for the "ethical" subscale of the FCQ and for the "environmental welfare" subscale of the SUS-FCQ. We will use the score with the highest Cronbach's coefficient in the analyses. The Food Choice Questionnaire will be complemented with questions regarding potential changes in food consumption habits that will inform future research work and will not be analysed as part of the present study. This latter was studied by (Gadema & Oglethorpe, 2011). Will follow, questions evaluating participants' declared capacity to make food choices based on the environmental impact or the nutritional quality of products.

<sup>3 These questions have the purpose to inform an additional research project.

4) A socio-demographic questionnaire to collect data regarding the participants (age, gender, level of qualification, etc.) will be completed by the participants.

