## EXPERIMENTAL DESIGN

[figure not shown]
This study will be a randomised controlled trial with two experimental arms:

[figure not shown]
- 1/ No label (no label condition)
- 2/ Environmental label (label condition)

A 2-block randomisation sequence (male and female) of 1:1 will be generated to allocate each participant to one of the experimental arm before recruitment using the Random Allocation software (Saghaei, 2004).

Each participant will be asked to perform two hypothetical shopping tasks in a virtual shopping environment, first in an "everyday scenario": 1/ choice of 3 ingredients for an everyday home-cooked dish among 66 products, 2/ choice of a ready-to-eat dish for an everyday meal among 30 products. The order of presentation of the two tasks will be counterbalanced. Then, the participants will be asked to perform the same two tasks while choosing foods for a dish that is "good for the planet" ("environmentally-friendly scenario"). For a given participant, the order of presentation of the two tasks will remain the same as in the everyday scenario.

The experimental design is described **Figure 1**.

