## PARTICIPANTS AND RECRUITMENT

### Recruitment

Participants will be recruited thanks to the "PanelSens" database from the "Chemosens" platform. This database was declared to the relevant authority (*Commission Nationale Informatique et Libertés; CNIL;* n°1,148,039). Participants will be invited to take part in a lab study that aims to study food choices in a virtual supermarket. After completing the study, participants will receive a 10-euro voucher.

The recruitment will be stratified on sex:

- 50% male
  - o 50% female

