## METHODS

## Online shopping tasks

### Shopping tasks

The experimental sessions will take place individually. After participants will have given their informed consent to take part in the experiment, they will be asked to sit down and will be equipped with a virtual reality headset. A qualified experimenter will be present to assist the participants.

The first step will consist in a test of the virtual environment so that participants can familiarise themselves with the virtual supermarket environment. Participants will be asked to navigate and test the functionalities of the virtual reality headset. This dummy supermarket will only include cosmetic products (shampoos, soaps, etc.).

Then, participants will start the shopping tasks under two scenarios. If participants are allocated to the "label condition", the label will be presented and explained to the participants prior to the shopping tasks with a pop-up message.

- For the first scenario, in the first task, we will ask the participants to navigate in the aisles of a virtual environment of 66 foods and to select 3 food items in order to prepare a home-cooked dish for an everyday meal. In the second task, the shopping environment will be composed of 30 foods and participants will be asked to select 1 ready-to-eat dish for an everyday meal. The order of these tasks will be balanced.
- 2) The second scenario will be broken down in the same two tasks. We will keep the same order for the two tasks as in the first scenario. This time we will ask the participants to choose foods for a meal that is "good for the planet".

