## Definition of the population for analysis

Participants who will be included in the statistical analyses are the ones having completed the shopping tasks and answered all of the questionnaires. Aim-guessers will be excluded in the sensitivity analysis.

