## Participant's characteristics

Participants' characteristics, overall and for each condition, will be displayed in a table. We will include gender, age, highest educational qualification, current employment, number of people living in the household, the perceived financial status of the household, dieting status and BMI. Continuous variables will be summarised using means and standard deviations. Categorical variables will be summarised using counts and percentages.

Objective	Dependent variables (Y)	Independent variables (x)	Data used	Statistical analysis
1.1. To study the effect of an environmental label on the environmental	Mean of PEF scores for 100g of each ingredient selected and PEF score for 100g of the ready- to-eat dish.	- Environmental label (0= no / 1= yes)	Only data from scenario 1 ("everyday scenario")	Mixed model analysis with random effect of participants. PEF = label (0/1) + type_of_food (I/RTEd) + label*type_of_food

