### Sensitivity analyses

- Sensitivity analysis will be carried out to analyse if the results found for MODEL 1.1. remain the same when aim guessers are excluded.
- **MODEL 1.1.** will be adjusted for age, sex, level of education and BMI.
- **MODEL 1.1.** (raw and adjusted) will be replicated for the GHGe from the Agribalyse database instead of the PEF score.

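### Aim-guessing is probed only after the 'good for the planet' scenario, so the Model 1.1 sensitivity analysis can exclude participants for what they learned after their everyday choices

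*Combined protocol and SAP*

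**What the plan says.** All references are to the combined protocol and SAP.

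- **Order of scenarios.** Under Experimental design and Shopping tasks, everyone completes the two everyday tasks first and then repeats both under a new instruction: "This time we will ask the participants to choose foods for a meal that is" good for the planet. Task order within a scenario is counterbalanced; scenario order is fixed.
- **Timing of the probe.** Under Questionnaires after the shopping experience, the first step comes when all shopping is finished: "After the four shopping tasks, participants will be asked to evaluate their familiarity and liking of the eight products selected". Next comes the step that matters here: "An investigation questionnaire will then be presented to participants on a computer to identify aim-guessers". The Study flow table gives the same order.
- **Use of the status.** Definition of the population for analysis states: "Aim-guessers will be excluded in the sensitivity analysis". Sensitivity analyses names the model: "Sensitivity analysis will be carried out to analyse if the results found for MODEL 1.1. remain the same when aim guessers are excluded".
- **Data in that model.** The overview table of the statistical analysis restricts Model 1.1: "Only data from scenario 1".
- **Earlier cues.** The invitation is neutral: "Participants will be invited to take part in a lab study that aims to study food choices in a virtual supermarket". Shopping tasks adds that, in the label arm only, a pop-up explains the label before any shopping.

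The plan does not define an aim-guesser, give the wording of the question, ask participants to recall what they suspected during the first scenario, or include an earlier probe.

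**The concern.** The check is meant to show whether the label effect on everyday choices is a demand effect, that is, whether it comes from people who had worked out the environmental aim while choosing. What matters is therefore what the participant suspected during the everyday tasks. The plan measures what the participant believes at the end of the session, after the protocol has named the environmental theme to everyone, and applies that answer backwards to choices made earlier.

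A control participant who suspected nothing while shopping for an everyday meal could reasonably mention the environment when asked at the end. If that counts as guessing the aim, the participant leaves the Model 1.1 rerun for a reason that could not have influenced the choices being analysed. This is the only planned analysis that addresses aim-guessing in the primary result. If the effect fades in it, readers may conclude that the finding was demand, when the cause could be lost numbers or the removal of environmentally minded participants.

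**Working it through.** **1. Sequence.** No arithmetic is needed.

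| Step | Label arm | No-label arm | Used in Model 1.1? |
|---|---|---|---|
| Invitation | neutral | neutral | – |
| Pop-up explaining the label | yes | no | – |
| Everyday tasks | done | done | yes |
| Instruction naming the planet, then the same tasks | done | done | no |
| Liking and familiarity ratings | done | done | no |
| Aim-guess probe | done | done | decides exclusion |

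The probe comes after an instruction that the analysed choices preceded. In the no-label arm, that instruction is the first environmental cue the documents describe.

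**2. The plan's power figure.** Inputs from Sample size: d = 0.50, alpha 0.05, 122 analysed, 130 recruited. Allocation is 1:1 (Experimental design). Sidedness is not stated; I assume two-sided. I use a two-sample t-test with d standardised on one value per participant, which simplifies the mixed model. Noncentrality is d × √(n/2), with 2n − 2 degrees of freedom.

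- 61 per arm: 0.5 × √30.5 = 2.76; power 78.2%, close to the stated 80%. Solving for 80% gives a total of 128. The point does not depend on this difference.
- 65 per arm: 0.5 × √32.5 = 2.85; power 80.8%.

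**3. Power after exclusion.** The plan gives no aim-guess rate, so the rate is an assumption. If 60% of each arm is excluded, 65 × 0.40 = 26 per arm remain: 0.5 × √13 = 1.80; power 42.4%. Starting from 122, exclusion of 10%, 20%, 40% or 60% gives 73.8%, 68.6%, 56.0% or 40.2%. The 8 extra recruits are an allowance for technical loss, not for this.

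**4. Who is excluded.** Let g be the share who suspected the aim by the end of the everyday tasks, and c the share of the others who name it only after scenario 2. Assume that everyone who names it is excluded. Then:

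- excluded share = g + (1 − g)c
- wrongly excluded, as a share of all excluded = (1 − g)c / [g + (1 − g)c]

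With g = 10% (assumed), starting from 122:

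| c | Excluded | Of these, wrongly | Left | Power |
|---|---|---|---|---|
| 10% | 19% | 0.09/0.19 = 47% | 99 | 69% |
| 30% | 37% | 0.27/0.37 = 73% | 77 | 58% |
| 50% | 55% | 0.45/0.55 = 82% | 55 | 44% |

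For g from 5% to 20% and c from 10% to 50%, the wrongly excluded share runs from 0.08/0.28 = 29% to 0.475/0.525 = 90%.

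**5. Can the estimate move as well?** This is a simulation with invented parameters. Environmental concern lowers the outcome by 0.3 SD per SD of concern. The label effect averages −0.50 SD and is larger in more concerned people. Naming the aim has no influence on choices, so any change after exclusion is an artefact.

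- Naming unrelated to concern or arm (38% excluded in each): −0.50 stays −0.50; only power is lost.
- Naming related to concern, equally in both arms (39% in each): −0.50 becomes −0.43.
- Naming related to concern and also commoner with the label (about 60% versus 38–39%): −0.50 becomes −0.34 or −0.26, and a true null becomes +0.05 or +0.12, against the hypothesis.

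The second case is the one that the shared scenario 2 instruction could produce without any help from the label. The third also needs the label to affect naming.

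**The case against.** The best reply is that the criterion is undefined, so the failure is not certain. The aim is the effect of a label on choices, and a strict rule, such as naming the label's effect, would catch few controls, who never see a label while shopping. The same questionnaire already asks about influences on choice separately for each scenario, so a scenario-specific aim question would fit. This stands in part. A reader might infer that everyone who mentions the environment will be excluded, or that all excluded participants owe their knowledge to scenario 2. The documents support neither: the exclusion can capture later knowledge, and the pop-up gives the label arm a cue before its everyday choices. But no strict or retrospective rule is written, and the order of events is.

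Three other strong readings also go too far.

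- **Unequal exclusion by arm.** A reader might blame the timing for it. Both arms get the scenario 2 instruction; an imbalance would come mainly from the label and pop-up, and would survive an earlier question.
- **A preserved effect means nothing.** Someone who guessed early would probably still say so at the end, so late probing errs mainly towards excluding too many. A preserved effect does not rule out demand, but that is true of any probe.
- **The primary result is compromised.** Primary Model 1.1 keeps aim-guessers.

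It is also fair to object that a question between the scenarios could send label participants back to the label just before scenario 2, which feeds Model 1.2, another primary objective. That is a real, small cost.

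**Conclusion.** The concern holds in a limited form. The documents fix the order of events, and with that order the probe cannot tell suspicion during the everyday tasks from knowledge supplied by scenario 2, most clearly in the no-label arm. The likely harm is over-exclusion: lower power (about 42% at d = 0.50 if 60% of each arm were excluded, against 81% with all 130) and a possible spurious loss of effect.

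The size is illustrative. It rests on assumed exclusion rates, a two-sided t-test and, for the shift in the estimate, assumed links between environmental concern, response to the label and naming the aim. The flaw in timing rests on none of these. Only one sensitivity analysis is affected, but the repair is cheap and should be made.

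**What to change.** Tie the aim question to the everyday scenario, in one of two ways.

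1. **Between the scenarios.** The experimenter already present asks one neutral open question about what the study seems to be about. Cost: a short pause and possible slight priming of scenario 2, hence of Model 1.2.
2. **First item of the investigation questionnaire.** An open question asks what the participant thought the study was about during the first shopping tasks, placed before any item that mentions the environment or the label. The plan does not currently state the item order, and controls are asked there about an environmental label. Cost: reliance on recall after scenario 2; scenario 2 itself is untouched.

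With either option, base the Model 1.1 exclusion on that answer only. Write down beforehand what counts as guessing the aim, and have the answers coded blind to arm. Report aim-guess counts by arm. Describe the result as coming from a non-randomised subset, because exclusion may still differ by arm owing to the label and pop-up. Neither option needs an extra visit or more participants, and the primary analysis stays as planned.

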### Exploratory analyses

Descriptive analyses of the answers to the investigation questionnaire will be performed.

1/ We will calculate the scores of participants responding to the following questions depending on the label condition and the scenarios ("everyday" / "environmentally friendly"):

• How much did taste / nutritional quality / environmental impact / packaging size / presumed price influence participant's food choice in the virtual supermarket? (5 possible answers ranging from "strongly disagree" to "strongly agree")

2/ We will calculate the scores of participants responding to the following questions depending on the label condition:

- What participants understood when asked to make food choices that are "good for the planet" (8 possible answers).
- Participant's perception of their capacity to distinguish 2 foods depending on their environmental impact (5 possible answers ranging from "strongly disagree" to "strongly agree").

3/ We will calculate the scores of participants, in the labelling condition, responding to the following questions:

- If they noticed the label (0=they did not notice the presence of the label on the products chosen or thought that the label was present on less than half of the products chosen /1=the participant thought the label was present on all of the products chosen or on more than half of them).
- If they understood the environmental label presented on the foods in the virtual supermarket (0=the participant did not answer correctly / 1=the participant answered correctly).
- If they used the environmental label when making food choices (we will categorize the scale ranging from 0 to 100 into 4 parts).

Further exploratory analyses will be conducted to have a broader understanding of the effects of the environmental label on food choices and are summarised in **Table 6**.

Data used of the analysis	Dependent variable	Independent variables	Statistical analysis
Both labelling conditions and the 2 scenarios will be considered	Importance of food choice motives for each scenario (taste, nutritional quality, environmental impact, presumed price and packaging size) Continuous variables	
 
Environmental label (0= no / 1= yes)
 
Scenario ("everyday scenario"/ "environmental-friendly scenario")
 
	

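### By the stated questionnaire order, no-label participants see the label before rating their capacity to judge foods by environmental impact, so that exploratory contrast is not against an unexposed control

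*Combined protocol and SAP*

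**What the plan says.** The section Questionnaires after the shopping experience gives a sequence: "These questionnaires will be presented in the following order". Item 1 is the rating of liking and familiarity under the headset. Item 2 is the investigation questionnaire on a computer. In it, participants in the no-label arm are asked whether they noticed an environmental label in the supermarket and "if they understand the meaning of the environmental label (displayed in the questionnaire". Participants in the label arm are asked whether they paid attention to the label, understood it and used it. The description of item 2 ends with: "We will also ask questions to investigate what participants understood when asked to choose an environmentally-friendly dish".

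Item 3 opens with "From this will follow a food choice motivation guestionnaire". After the food choice scales and some questions on consumption habits, it closes with "questions evaluating participants' declared capacity to make food choices based on the environmental impact or the nutritional quality of products". The Study flow table shows the same order: investigation questionnaire, then food choice questionnaire, then socio-demographic questionnaire.

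The section Exploratory analyses plans to calculate scores of participants "responding to the following questions depending on the label condition". Two items are listed there. One is what participants understood by the environmentally friendly instruction. The other is "Participant's perception of their capacity to distinguish 2 foods depending on their environmental impact", on a five-point agreement scale.

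**The concern.** A tabulation by label condition invites the reader to treat the no-label arm as people who never met the label. For perceived capacity, the stated order does not deliver that. Controls have been shown the label and prompted to interpret it shortly before they rate themselves.

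The plan's own reasoning makes this relevant. The Background argues that such labels may add to consumers' knowledge of environmental impact, and the traffic-light format was chosen because it is thought to aid understanding. A label expected to inform cannot be assumed to leave the next self-rating untouched. A small difference between arms would then have two readings: shopping with the label does little for perceived capacity, or the display moved the controls. What is at stake is the interpretation of one descriptive exploratory table.

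**Working it through.** The plan gives no figure on this point, so the check sets the sections side by side.

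1. **Who is exposed.** Item 2 names no subset of the no-label arm, so the display applies to all controls. With 1:1 allocation (Experimental design) and 130 recruited (Sample size), that is 130 / 2 = 65 people, approximately.
2. **When they are exposed.** The display is in item 2. Item 3 follows item 2, and the questions on "declared capacity to make food choices based on the environmental impact or the nutritional quality of products" are at the end of item 3. Exposure therefore precedes the capacity rating.
3. **What is compared.** Exploratory analyses splits perceived capacity by label condition. Only the environmental item is listed there; the nutritional one is not.
4. **What the two arms have met by then.** The label arm had the label explained in a pop-up before shopping (Shopping tasks) and shopped with it on the products. The no-label arm has seen it once, in a questionnaire. Exposure is unequal, but it is not zero in either arm.
5. **Whether the position is certain.** Exploratory analyses introduces its list as answers to the investigation questionnaire, which is item 2. It also speaks of distinguishing two foods, where item 3 speaks of making food choices. If these are two different items, the tabulated one sits in item 2 and its order relative to the display is not stated. Item 3 is the only text that gives capacity questions a position. On either reading, the plan does not secure an answer given before exposure.
6. **What lies upstream of the display.** All product choices, and hence PEF, FSA, NOVA and price, are made before item 1. Liking and familiarity are rated in item 1. None of these outcomes can be affected.

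**Size (assumptions only).** Let D be the true arm difference in the share who agree, without any display to controls, and c the fraction of it that the display carries to controls. The observed difference is (1 − c) × D. Neither D nor c is in the documents. Taking D = 20 points for illustration:

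| c | Observed difference |
|---|---|
| 0 | (1 − 0) × 20 = 20 points |
| 0.25 | (1 − 0.25) × 20 = 15 points |
| 0.50 | (1 − 0.50) × 20 = 10 points |
| 0.75 | (1 − 0.75) × 20 = 5 points |

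If the display lowers controls' confidence, c is negative and the observed difference exceeds 20 points. The table shows how the contrast would respond; it does not estimate a bias.

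**The case against.** The strongest reply is that little depends on this. The item is descriptive and exploratory, no test is specified for it, and no objective or hypothesis concerns perceived capacity. That is correct, and it keeps the point minor. It does not remove it, because the plan still intends to show the item by arm.

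A second reply is that one unexplained display is far weaker than shopping with an explained label. That also stands. A reader might infer that the control group is lost for this comparison, but the documents do not support that: the difference between shopping with and without the label is intact, and only the reference level has changed.

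A reader might also infer that the item on what an environmentally friendly dish was taken to mean is contaminated in the same way, because it is described after the display. The plan orders the questionnaires, not the items inside one, so that item's position relative to the display is simply not stated.

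Finally, a reader might infer a bias towards no difference. That is plausible but not derivable. The Background also reports that many consumers found such labels hard to understand and use, so a display without explanation could lower controls' self-ratings and widen the gap.

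A practical objection concerns the remedy. Moving every label item behind the whole food choice questionnaire (24 items plus 5 on environmental welfare) would delay noticing and use, which are predictors in the further exploratory models, and would place them after much environment-related content. This is a good reason for a narrow reorder.

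**Conclusion.** The point holds as a minor one. It rests on the only stated position of the capacity questions, and on the tabulated capacity item being one of them. On that basis, every control has seen the label, and been asked its meaning, before the self-rating that is compared by arm. The contrast should be read as label use while shopping against one questionnaire display. Its bias is of unknown sign and size. Two gaps in the text need closing whatever the answer: the capacity item is placed differently in two sections, and the order of items within the investigation questionnaire is not given.

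**What to change.** In both arms, ask the capacity items and the item on understanding of an environmentally friendly dish before any item that names or displays the label. Put the label items (manipulation check, noticing, understanding, use) directly after them, and otherwise as early as they are now, ahead of the food choice scales. Keep the aim-guessing question ahead of the moved items, so that they do not give it away.

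State this item order in Questionnaires after the shopping experience and in Study flow. Make Exploratory analyses name the same capacity item, with the same wording and the same questionnaire.

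The cost is a change of question order in Qualtrics and a few lines of protocol text, with no new items. The downside is small: label noticing and use are asked slightly later, after a few environment-related questions.

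If data collection has begun, leave the order as it is and report the contrast as shopping with the label versus a single display in a questionnaire.
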